- 13. Certainty about the decision will be measured using the Decisional Conflict Scale (DCS): The DCS⁷⁰ has an initial question to ascertain the option that has been selected. Options presented will be: continue [medication regimen from experiment], resume previous medication/dosage, conduct another experiment, return to pediatrician to adjust dosage or change medication, other [write in]. The DCS then has 16 questions that are divided into five subscales: informed subscale, values clarity subscale, support subscale, uncertainty subscale, and an effective decision subscale. The informed subscale measures how informed participants feel about the benefits and risks of the decision. The values clarity subscale measures a participant's feelings about personal values for benefits and risks/side effects. The support subscale measures perceived levels of support during decision-making. The uncertainty subscale measures a participant's level of certainty about the best choice to make. The effective decision subscale measures the satisfaction with the decision made. The total DCS score equally weighs all five subscales. Responses to each question are reported on a 5-point Likert scale (0 = strongly agree to 4 = strongly disagree). The total DCS scores are calculated by summing item scores and then converting the scores to a 0-100 scale, where 0 implies no decisional conflict and 100 implies extremely high decisional conflict. Scores <25, 25 to 37.5, >37.5 indicate low, moderate and high decisional conflict, respectively. Scores 25 and higher reflect clinically significant decision conflict.
- 14. Behavioral Intention questions that will assess the adolescent and parent intention to take/give ADHD medicine regularly will be measured using the standard measure of intention from the UTBC. 46 Responses are on a 7-point scale from strongly agree (+3) to strongly disagree (-3) that assess intention to take medicine for ADHD on weekdays, weekends, and school vacations.
- 15. System Usability Scale (SUS)⁷¹ is a validated 10-item unidimensional scale with response options on a 5-point agreement scale which results in a score from 0 to 100, with higher scores indicating greater usability.

Implementation of decision: 3 months after study visit 2, we will obtain pharmacy dispensing records to ascertain whether their joint decision was implemented. If medication was continued, we will calculate the percentage of days covered.

DATA ANALYSIS

We will conduct descriptive analyses to summarize measures that characterize the sample in terms of demographic, ADHD, and psychosocial factors, the experiments selected, and decisions made, as well as feasibility and usability data. In order to determine overall feasibility and usability of our pilot intervention, we will compare retention, participation, and usability ratings to a priori criteria based on previous research (i.e., retention $\geq 80\%$, participation $\geq 80\%$, usability ≥ 70), 72 using Chi-square tests.

Power and Sample Size

We selected a target sample size of 30 to exceed the recommended sample size (n = 20) for a pilot trial designed to inform a larger efficacy trial with 80% power to detect a medium effect. Of note, we aren't powering the study to examine differences in outcomes by experiment type. Paired-samples t-tests will be used to calculate the change in DMIS,DCS, and behavioral intentions for all adolescents and parents, and for medication continuity among the subset who choose to continue medication after completing their experiment. Cohen's d will be calculated to estimate effect size for each pre- to post-outcome and interpreted as small (.20), medium (.50), and large (.80).

Hypothesis testing

We will test the following hypotheses:

- 1. From pre to post, within-subject report on DMIS subscales "child express" will increase and "parent seek" will increase.
 - a. Paired sample t-test
- 2. From pre to post, within-subject DCS will decrease.
 - a. Paired sample t-test
- 3. Higher post-DMIS joint/decision scores will be reported by dyads who differ on initial preferences following the experiment compared to those who don't.
 - a. Two sample t-test
- 4. Higher post-child express scores will be reported by adolescents who want to make the decision alone compared to those who prefer to share decision or have parent make decision.
 - a. Two-sample t-test
- 5. Adolescent-parent conflict as measured at baseline by the CBQ will be positively associated with discordance in independent preferences following the medication experiment.
 - a. Biserial correlation coefficient
- 6. The difference between the adolescent's intention to take ADHD medication and the parent's intention to give ADHD will decrease from pre to post.
 - a. Linear mixed model

Scientific Rigor:

An open label trial is an appropriate design to test the feasibility, acceptability, and preliminary efficacy of the medication experiment intervention and therefore warrants further testing in a future larger trial. Our preliminary data strongly supports the importance of the problem, intervention targets identified, and the feasibility of the approach in our hands.

FACILITIES

Cincinnati Children's Hospital Center for ADHD is the performance site for this study.

POTENTIAL BENEFITS

Although we cannot guarantee a benefit to any individual participating adolescent or parent, medication experiments are recommended in clinical practice guidelines to help resolve uncertainty about continued medication use. Benefits of the study outweigh any potential risks because this intervention will likely improve care.

POTENTIAL RISKS, DISCOMFORTS, INCONVENIENCES, AND PRECAUTIONS

There is minimal risk to the participants in this study. For dyads who select a medication experiment involving not taking medicine for some period of time, it is possible the adolescent could experience more ADHD symptoms than usual and/or a decline in functioning. Indeed, adolescents often experience such effects when conducting impromptu experiments without physician supervision. For dyads who select a medication experiment involving taking medication on additional days (e.g., non-school days) or trying a different medication or dosage, it is possible the adolescent could experience side effects which s/he may or may not have experienced in the past. Both of these scenarios are the reason why clinical practice guidelines recommend that medication experiments are personalized, structured, and physician supervised. Dyads will be able to reach the study team between visits with any concerns. Medication experiments will end early if needed.

Because confidential information about study participants will be available to study staff, procedures to safeguard the confidentiality of this information are required. Several safeguards will be put in place. Electronic data will be protected by username and password requirements. All data collected on adolescents and parents will be assigned a unique code that will be linked to identifying information. The master coding sheet that will link the information will be kept in the study coordinator's office under lock and key. In addition to assuring confidentiality of the research data, it is also critical that the confidentiality of the patient's clinical information is protected in mehealth for ADHD. The HIPAA regulations and their application to this product are clearly defined to ensure compliance within their guidelines. Mehealth for ADHD was designed with a procedure for encrypting and storing the data in such a manner to only allow pediatricians to view identifiable data. This design employs a key-based encryption structure. This method does require extra security information to be maintained by the parties who are encrypting the data. For example, parties needing access to the data are assigned a "key" that is used to encrypt and decrypt the data in addition to a user ID. Such a key will be maintained by the PI and kept under lock and key. Implementation of additional methodologies to keep confidential information off the server will be implemented including such methodology as ensuring the CCHMC server is secure (i.e., firewalled).

PROTECTION OF VULNERABLE POPULATION

Because adolescent children are being invited to participate in the study, the following procedures will be followed to avoid issues related to coercion or undue influence. First, study staff will review the assent form with participating adolescents, in language appropriate for their intellectual functioning and developmental levels, and ask whether or not the adolescent agrees to participate. Similarly, they will be told that they can opt not to participate or answer any questions which they do not want to answer at any time. This will be re-iterated whenever necessary.

RISK/BENEFIT ANALYSIS

The risks to participants are minimal and unlikely, largely stemming from the possibility of loss of confidentiality. We have instituted provisions to minimize this risk and will assure participants of the voluntariness of their participation and their right to withdraw participation at any time. We will also take appropriate steps to safeguard confidentiality. We suggest that this study falls under the "Minimal Risk" category.

ALTERNATIVES

Participation in the present study is completely voluntary. The alternative to participation in the study is to choose not to participate in the study.

DATA SAFETY & MONITORING

Adolescents and parents who agree to will receive access to a version of the mehealth for ADHD that has been enhanced with new intervention components. Given that the risks to participants are minimal, there does not appear to be the need for an external monitoring board. Rather, [name] (PI) will assume primary responsibility for the ongoing monitoring of the data and safety of the study, and will provide reports of this with the annual renewal application to the IRB and annual progress report to the sponsor. [name] is an expert in ADHD management and ADHD research, and has experience conducting research such as that proposed in this application. [name] has medical expertise related to pharmacotherapy of children with ADHD to address study-related medical issues. All research staff will complete education in the protection of human research subjects.

[name] will continuously evaluate the project's performance, safety, and need to stop. Performance will be monitored by examining subject recruitment, comparison with targeted recruitment retention, protocol adherence, and quality of data collection procedures. This will primarily be accomplished in weekly staff meetings attended by Drs. [name].

[figure not shown]
[name] will be available at all times to address any safety issues. Any serious adverse events will be determined by [name] and reported to the IRB within 24 hours, specifying the nature of the event and outcome, if related to the study and if anticipated or not. If a serious adverse event as a result of participation in the study occurs, recruitment will be immediately discontinued until the serious adverse event has been reported to the IRB and the IRB has deemed it appropriate for the study to continue.

COST OF PARTICIPATION

There will be no costs to the subject for participating in this study. The study physician will provide prescriptions, as needed, during trial participation, but participants will be responsible for obtaining ADHD medication from their pharmacy as they do for typical clinical care.

PAYMENT FOR PARTICIPATION

Each parent/adolescent dyad will be compensated \$50 for survey completion and \$100 for completing each study visit. They will additionally receive up to \$100 for time spent submitting data during the medication experiment . This will be pro-rated based on the % of days with complete data reported over days expected. For example, if the medication experiment lasts for 6 weeks and both parent and adolescent entered data for 34 out of the 42 days, they would receive 80.9% of \$100 = \$80.90. Therefore the maximum total compensation throughout the study is \$350.

References

- 5. [name] WB, Sherman SN, Zmitrovich AR, et al. In their own words: adolescent views on ADHD and their evolving role managing medication. Research Support, N.I.H., Extramural Research Support, Non-U.S. Gov't. *Acad Pediatr*. Jan-Feb 2012;12(1):53-61. doi:10.1016/j.acap.2011.10.003
- 6. Pliszka S. Practice parameter for the assessment and treatment of children and adolescents with attention-deficit/hyperactivity disorder. *J Am Acad Child Adolesc Psychiatry*. Jul 2007;46(7):894-921.

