dispensing data. During the visit, parents and adolescents will receive training on how to use mehealth for ADHD and will choose one of the five medication experiments to complete together and track the effects for the desired amount of time. Once dyads have completed the medication experiment, they will complete a follow-up study visit to review the results from the experiment, discuss feasibility of the software, and complete end of study measures.

Figure 2.

^{*}Electronic baseline surveys: Demographics, Health-Care Literacy Scale, Vanderbilt Scale/ADHD Self-report, Columbia Impairment Scale, Pittsburgh Side-Effect Rating Scale, Pre-Intention Factors, Medication Barriers, Behavioral Intention, Conflict Behavior Questionnaire, and (adolescents only) Medication Diversion

DURATION:

This IRB protocol covers the phase of the study during which we will test the medication experiment feature developed in collaboration with our stakeholders during the first phase of the study. Families can customize the start and end date as well as the amount of time they track effects in the medication experiment. Thus, families could be enrolled in the study for up to 4-

months. We expect that all 30 dyads will be recruited and complete the study participation over the course of one year.

PROCEDURES:

Research Participant Recruitment and Obtaining Informed Consent

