Subsequently, the adolescent and parent will be asked to independently indicate the option they expect to prefer after the experiment ends (continue [medication regimen from experiment], resume previous medication/dosage, conduct another experiment, return to pediatrician to adjust dosage or change medication, other), their certainty about the decision, and their preferred role in decision-making (see Measures).

The study physician will confirm that there are no cardiac risk factors (adolescent history of heart disease, family history of sudden death in children, hypertrophic cardiomyopathy, long QT syndrome) that might preclude the use of stimulant medications and complete a brief physical exam. The adolescent's pediatrician likely assessed this prior to starting stimulant medication.

All medication experiments involving a change in medication regimen will involve tracking outcomes for 2 weeks on their current regimen and a minimum of 2 weeks after making a change. We will partner with dyads to select the order, typically starting with current regimen. In randomized controlled trials of ADHD medication discontinuation, relapse is typically noticed

within 2 weeks.⁴⁹ Hence, we are confident that most participants won't require repeated cycles of treatment and non-treatment as classically described in the N-of-1 trial literature.⁵⁰ Dyads will be able to reach the study team between visits if untoward effects (e.g. relapse of symptoms/impairment, side effects, etc.) convince them to end the experiment early and/or resume their previous regimen. We will follow best practices for medication experiments recommended in ADHD clinical practice guidelines^{6,7} These include conducting when there are few transitions or demands (i.e. mid school year), and avoiding at beginning of any school year, especially at the start of middle school or high school. The trial on/off medicine is designed to reduce ambivalence about medicine (i.e. document improvement among adolescents who still benefit) which may motivate self-directed changes to support medication continuity.

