Symptom & side effect monitoring: The mehealth for ADHD software enables the tracking of ADHD symptoms, medicine side effects, and other outcomes that are important to adolescents and parents. In addition, adolescents and parents can construct their own measures using a structured approach with examples to ensure that adolescents and parents can translate what matters most to them into a measure that can be tracked over time. For example, an adolescent could decide to record the presence of a relevant side effect (e.g. irritability) on a daily basis. A parent could decide to track the time spent completing homework every night. It is important to note that parents and adolescents may track different outcomes. This reflects differences in what's important to them as well as differences in what they are best positioned to report on. For example, only adolescents can report on how the medicine makes them feel. Only parents can report on what they observe. Adolescents and parents can report on their chosen outcomes via an internet survey that has been optimized for completion on a mobile screen. The system provides reminders to adolescents and parents to rate targeted outcomes by cell phone text messages. The research assistant and study physician will also be available by phone to answer questions and/or address concerns that arise.

We will monitor on-going medication experiments for each dyad and will be available if questions or concerns arise. We will additionally reach out to parents if we identify any difficulties using the website.

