At the conclusion of the medication experiment, the research assistant will schedule an inperson study visit at the Center for ADHD. The study physician, adolescent and parents will discuss what was learned using a report generated by mehealth for ADHD to visualize the outcome data that was collected. Subsequently, the adolescent and parent will be asked to independently indicate their preference for what to do next (continue [medication regimen from experiment], resume previous medication/dosage, conduct another experiment, return to pediatrician to adjust dosage or change medication, other), and their preferred role in decision-making. The study physician will then facilitate a discussion to resolve any differences between adolescent and parent preferences and come to a consensus. The parent will receive a study summary document to share with their child's pediatrician so s/he is aware of what was learned and can use this to guide future management decisions. The adolescent and parent will report this decision, their certainty about the decision, their preferred role in decision-making, their involvement in the process of making this decision, and their intentions about taking/giving medicine. We will also ask the parent and adolescent about the usability the medication experiment software (see Measures).

Measurement Strategy: Aggregation of individual trials to estimate a population level treatment effect isn't needed given the strong evidence of stimulant effectiveness among adolescents.¹ Rather, it is important to ascertain whether the use of medication experiments helps adolescents and parents work together to resolve uncertainty about future use of medicine. We will describe the type and number of medication experiments conducted as well as the personal outcomes selected for tracking. We will examine process outcomes like the decision-making involvement, comfort with the decision made, and whether the decision was implemented.

Measures to characterize the sample on demographic, ADHD, and psychosocial factors

- 1. Demographics: Adolescents, parents, and pediatricians will report on age and race/ethnicity. Parents will also report on child insurance status, and their own level of education and mental health history.

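### The symptom, impairment and side-effect scales are scheduled at baseline only, so the pilot will give no systematic, comparable data on the non-serious harms that the protocol itself names

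*Combined protocol and SAP*

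**What the plan says.** **Harms named.** Potential Risks, Discomforts, Inconveniences, and Precautions says that for experiments with time off medicine "it is possible the adolescent could experience more ADHD symptoms than usual and/or a decline in functioning". For experiments that add medication days or try another medication or dosage, it names side effects.

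**When the matching scales are given.** The Figure 2 footnote in Study Design reads "Electronic baseline surveys: Demographics, Health-Care Literacy Scale, Vanderbilt Scale/ADHD Self-report, Columbia Impairment Scale, Pittsburgh Side-Effect Rating Scale" and goes on to other questionnaires. In the measures section the same instruments (Vanderbilt and ADHD self-report, Columbia, Pittsburgh) stand under "Measures to characterize the sample on demographic, ADHD, and psychosocial factors".

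**What is collected at the end.** The visit 2 description in Intervention covers preference, decision, certainty, role, involvement, intention and usability. Outcome Measures lists the Decision-Making Involvement Scale (DMIS), the Decisional Conflict Scale (DCS), behavioral intention, the System Usability Scale (SUS) and later dispensing records.

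**What is collected in between.** Under Symptom & side effect monitoring, the software makes symptom and side-effect tracking possible. By way of example, "an adolescent could decide to record the presence of a relevant side effect". The text then says "Adolescents and parents can report on their chosen outcomes via an internet survey", and parent and adolescent may choose differently. The physician and research assistant help set the targets.

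**Risk statement.** Risk/Benefit Analysis says "The risks to participants are minimal and unlikely, largely stemming from the possibility of loss of confidentiality".

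**The concern.** A pilot of supervised medication changes in 11- to 15-year-olds should show how often those changes cause trouble. Here the instruments for the three named harms exist, and every dyad that reaches visit 1 has completed them, because visits are not scheduled while survey data are missing. The text does not schedule them again. A post-change value for a non-serious harm then exists in structured form only where that harm was among the targets the dyad elected to track.

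Two uses are affected. Purpose of Study presents the pilot as the basis for further testing in a larger trial, and Potential Benefits asserts that benefits outweigh risks. Data Safety & Monitoring gives minimal risk as the reason for having no external board. Neither judgement will be informed by systematic harm data from this trial. A severe but non-serious side effect could leave no entry in the dataset.

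**Working it through.** The protocol states no harm rate or safety sample size, so there is no figure to reproduce. The check is a comparison of sections, followed by an illustration.

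**1. Each named harm against its measurement.**

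| Harm named in Potential Risks | Scale in the plan | Baseline | Visit 2 or Outcome Measures list | During experiment |
|---|---|---|---|---|
| More ADHD symptoms | Vanderbilt (parent), ADHD self-report | yes | not listed | elective |
| Decline in functioning | Columbia Impairment Scale | yes | not listed | elective |
| Side effects | Pittsburgh Side Effects Rating Scale | yes | not listed | elective |

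Behavioral intention is a useful contrast. It appears in the baseline footnote and again in both the visit 2 description and Outcome Measures. Where the plan means to repeat a baseline measure, it says so.

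**2. Is tracking of harms required?** Experiments that change the regimen need 2 weeks of tracking before the change and at least 2 weeks after it. The text does not say which outcomes must be tracked, and no minimum set is given.

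**3. Is a harms analysis planned?** Data Analysis covers sample description, experiments chosen, decisions, feasibility, usability and six hypotheses. Measurement Strategy plans to describe which outcomes families selected. Neither mentions side effects, worsening, adverse events or early endings.

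**4. Who is exposed?** Of the five experiments, option 1 changes nothing. Potential Risks ties worsening to time off medicine (options 3 and 4) and side effects to added days or a new medication or dose (options 2 and 5). The number at risk of each harm is therefore unknown and probably below the 30 enrolled.

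**5. Illustration: zero events among n assessed.** The one-sided 95% upper bound is 1 − 0.05^(1/n).

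- n = 30: 1 − 0.05^(1/30) = 9.5%
- n = 24 (30 × 0.80): 11.7%
- n = 15 (30 × 0.50): 18.1%
- n = 10: 25.9%
- n = 8 (30 × 0.25 = 7.5, rounded up): 31.2%

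The shares are assumptions. The same formula applies to any smaller exposed group: if 20 were exposed and half of them tracked the harm, n = 10 and the bound is 25.9%.

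**6. Illustration: chance of recording at least one case.** With true rate p and tracking share q among 30, this is 1 − (1 − pq)^30. For an assumed p = 10%:

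- q = 1: 1 − 0.90^30 = 96%
- q = 0.5: 1 − 0.95^30 = 79%
- q = 0.25: 1 − 0.975^30 = 53%

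Steps 5 and 6 assume that the choice to track is unrelated to the harm. With elective tracking that is doubtful, and the direction of any bias is unknown.

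**The case against.** Much can be said for the plan.

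- **Other routes exist.** Serious adverse events go to the IRB within 24 hours. Staff follow ongoing experiments, dyads can contact the team about relapse or side effects, the physician reviews results in person at visit 2, and the principal investigator evaluates safety continuously, with weekly staff meetings. A reader might infer that harms are recorded only if a family chooses to track them; the documents do not support that. What remains is that no form, log or planned summary of non-serious events is described, and the visit 2 discussion rests on a report of the tracked outcomes.
- **Families do not choose alone.** Staff help set targets, and the software offers symptom and side-effect tracking before it offers self-built measures. This makes capture more likely but does not require it.
- **The risk statement is a prospective classification for the IRB.** The aims are feasibility, acceptability and preliminary efficacy. No safety objective is promised and then missed. This stands, and it limits the point to the absence of data that could check the classification.
- **Relapse timing.** The Intervention section says "In randomized controlled trials of ADHD medication discontinuation, relapse is typically noticed" within 2 weeks. A reader might take this as an expectation that relapse is common, in contradiction of the word unlikely. It gives timing, to justify the length of the experiment, and no incidence.
- **Individual targets are deliberate.** Parents found the Vanderbilt scales lacking in salience, and Measurement Strategy sees no need to aggregate individual trials. That argument concerns stimulant effectiveness and does not cover harms of the experiment, which is the intervention being piloted.
- **Part of the plan cannot be seen.** Figure 2 and the Compendium of Measures are not available here, and Study Design mentions end-of-study measures without listing them. This is a real limit. The two written lists nevertheless agree in omitting the scales.

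**Conclusion.** The point holds in a limited form. As far as the text can be read, the standard scales for the three named harms are baseline measures only, structured recording of non-serious harms after a change is elective, and no harms summary is planned. The existing safety routes serve individual care and serious events. They do not give comparable data across dyads.

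It would go too far to say that the trial contradicts its own risk statement or leaves participants unmonitored. Potential Risks discloses the clinical harms, and Risk/Benefit Analysis says risk stems largely, not solely, from confidentiality. The two sections differ in emphasis and should be reconciled.

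The size cannot be fixed from the documents. The bounds from 9.5% to 31.2% rest on assumed numbers assessed. Even full assessment would probably not reach 9.5% for a single harm, since not all 30 will be exposed to it. The point is worth acting on before the pilot is used to plan a larger trial. It does not bear on the validity of the decision-making outcomes.

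**What to change.** 1. Repeat the Pittsburgh scale electronically at visit 2, or when an experiment ends early, worded to refer to the period on the changed regimen. Do the same with the Vanderbilt/ADHD self-report and Columbia scales if burden allows. If repetition is already intended, list the scales under visit 2 and Outcome Measures.
2. Log non-serious events raised by contact or at visit 2, and record each early ending with its reason.
3. Add to Data Analysis a descriptive harms summary by experiment type: change from baseline, number with newly moderate or severe side effects, and early endings by reason. Use as denominator the number exposed to each type of change, and state how many of them were assessed.
4. Reconcile Risk/Benefit Analysis with the clinical harms named in Potential Risks.

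**Cost.** Protocol wording and re-use of existing electronic forms. The full set adds 13 + 13 + 18 = 44 adolescent items plus the parent versions, to a visit that already carries 30 + 16 + 10 = 56 items (DMIS, DCS, SUS) and the intention questions. Repeating the Pittsburgh scale alone adds 13 items per respondent. No treatment rule changes.
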